#### 6.8. Treatment Compliance

No analysis for treatment compliance is planned for this study.

#### 6.9. Important Protocol Deviations

Protocol deviations will be identified throughout the study. Important protocol deviations are

defined as those deviations from the protocol likely to have a significant impact on the

completeness, accuracy, and/or reliability of the study data or that may significantly affect a subject's rights, safety, or well-being.

The listing of important protocol deviations for all randomized patients during the entire study, with the indication of whether to be excluded from the PP population, will also be provided.

#### 6.11. Efficacy Analyses

#### 6.11.1. Primary Outcome and Methodology

The primary objective of this study (H1) is to test the hypothesis that LY900014 is noninferior to insulin lispro on glycemic control (NIM=0.4% for HbA1c) in patients with T1D, when administered as prandial insulin (0-2 minutes prior to the meal), in combination with basal insulin for 26 weeks.

The primary efficacy comparison will be based on the contrast between LY900014 and insulin lispro at Week 26 (Visit 18) from the MMRM analysis of change from baseline in HbA1c including data collected from all randomized patients prior to discontinuation of IP through Week 26. The model for the analysis of the primary efficacy endpoint of change from baseline in HbA1c will include the fixed class effects of treatment, strata (country, type of basal insulin, use of metformin at study entry), visit, and treatment-by-visit interaction, as well as the continuous, fixed covariates of baseline value. An unstructured covariance structure will be used to model the within-patient errors. Significance tests will be based on LS means and Type III tests. If this analysis fails to converge, the following covariance structures will be tested in order:

- Toeplitz with heterogeneity
- autoregressive with heterogeneity
- compound symmetry with heterogeneous variances
- Toeplitz
- autoregressive
- compound symmetry without heterogeneous variances

The first covariance structure that converges will be used. The Kenward-Roger approximation will be used to estimate denominator degrees of freedom.

LY900014 will be declared noninferior to insulin lispro if the upper limit of the 2-sided 95% CI for the LS mean difference in the change from baseline in HbA1c for LY900014 minus insulin lispro is below +0.4%.

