A graphical approach for multiple comparisons (Bretz et al. 2011) will be used to strongly control the overall Type I error (2-sided alpha level of 0.05) for testing the treatment effect for the primary and multiplicity adjusted objectives.

Baseline is defined as the last nonmissing measurement at or before the randomization visit, (Visit 8) unless otherwise specified.

The primary analysis method will be a restricted maximum likelihood-based, mixed-effect model repeated measure (MMRM) analysis using all the longitudinal observations at each scheduled postbaseline visit. The model for the analysis of the primary efficacy endpoint of change from baseline in HbA1c will include the fixed class effects of treatment, strata (country, type of basal insulin, and metformin use at study entry), visit, and treatment-by-visit interaction, as well as the continuous, fixed covariate of baseline value. For analyses of variables other than HbA1c, the HbA1c stratum (\leq 8.5%, >8.5%) will be included in the model. An unstructured covariance structure will be used to model the within-patient errors. Significance tests will be based on least squares (LS) means and Type III tests. SAS PROC MIXED will be used to perform the analysis. If this analysis fails to converge, the following covariance structures will be tested in order:

- Toeplitz with heterogeneity
- Autoregressive with heterogeneity
- Compound symmetry with heterogeneous variances
- Toeplitz

- Autoregressive
- Compound symmetry without heterogeneous variances.

The first covariance structure that converges will be used. The Kenward-Roger approximation will be used to estimate denominator degrees of freedom.

An analysis of covariance (ANCOVA) model for the change from baseline to the Week 26 HbA1c endpoint with strata (country, type of basal insulin, and metformin use at study entry), and treatment as fixed effects and baseline as a covariate will be conducted as supportive analyses. Missing endpoints will be imputed using the last-observation-carried-forward (LOCF) approach, using only postbaseline data. For analyses of variables other than HbA1c, the HbA1c stratum ($\leq 8.5\%$, $\geq 8.5\%$) will be included in the model.

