#### 5.2. Determination of Sample Size

Patients will be randomized in a 1:1 ratio to double-blind LY900014 dosed 0 to 2 minutes before meals, or double-blind insulin lispro dosed 0 to 2 minutes before meals. Assuming a noninferiority margin (NIM) of 0.4%, no true difference between treatment arms, and a standard deviation (SD) of 1.1%, approximately 298 completers (149 in each treatment group) will provide 87% power to show noninferiority between LY900014 and insulin lispro in change from baseline to 26 weeks in hemoglobin A1c (HbA1c) using the upper limit of a 2-sided 95% confidence interval (CI; LY900014 – insulin lispro). Assuming a 15% dropout rate for 26 weeks, approximately 350 patients will need to be randomized.

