# Table 6.2.Baseline and Postbaseline Definitions and Patient Population by
Study Period and Type of Analysis

Study Period/Analysis	Patient Population	Baseline Observations	Postbaseline Observations
Lead-In Period			

TEAEs	All Enrolled Patients	Prior to first dose of open-label insulin lispro (or Visit 2 date if the dose date is missing)	The entire lead-in period after first dose of open-label insulin lispro and prior to the first dose of IP (or Visit 8 date if the dose date is missing)
Basal, prandial, and total insulin doses, and prandial/total insulin dose ratio	All Randomized Patients	Visit 2	Visits 3–8 prior to initiation of IP
Weight MMRM and ANCOVA	All Randomized Patients	Last of Visits 1-2	Visits 3–8 AND Last of Visits 3-8
26-Week Treatment P	Period (including Safety	Follow-Up Visit wher	e applicable)
HbA1c MMRM and ANCOVA	All Randomized Patients with a baseline and at least 1 postbaseline observation while on IP	Last of Visits 7-8	Visits 11, 13, 15, and 18 prior to discontinuation of IP AND Last of Visits 9-18 prior to discontinuation of IP

Study	Patient Population	Baseline	Postbaseline Observations
Period/Analysis		Observations	
HbA1c categorical analyses longitudinal logistic regression and LOCF logistic regression	All Randomized Patients with a baseline and at least 1 postbaseline observation while on IP	Last of Visits 7-8	Visits 11, 13, 15, and 18 prior to discontinuation of IP AND Last of Visits 9-18 prior to discontinuation of IP
1-hr and 2-hr PPG and other MMTT variables	All Randomized Patients with a postbaseline observation while on IP	Visit 8 prior to initiation of IP	Visit 18 prior to discontinuation of IP
10-point SMBG, basal, prandial, and total insulin doses, prandial/total insulin dose ratio	All Randomized Patients with a baseline and at least one postbaseline observation	Visit 8 prior to initiation of IP	Visits 15, and 18 prior to discontinuation of IP AND Last of Visits 9 to 18 prior to discontinuation of IP
1,5-AG	All Randomized Patients with a baseline and at least 1 postbaseline observation	Visit 8 prior to initiation of IP	Visits 11, 15, and 18 prior to discontinuation of IP AND Last of Visits 9-18 prior to discontinuation of IP
Health outcomes: ITSQ, EQ-5D-5L, EQ-VAS, WPAI-GH	All Randomized Patients with a baseline and a postbaseline observation	Last of Visits 1-8	Last of Visits 9-18 prior to discontinuation of IP

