#### 6.2. Adjustments for Covariates

Stratification will be by country (China vs. Other), HbA1c stratum ( $\leq 8.5\%$  vs. >8.5% at baseline), type of basal insulin during the lead-in period (glargine U-100 vs. degludec U-100), and use of metformin at study entry (yes vs. no). Stratification factors will be entered into the IWRS for randomization and also collected in the database by electronic case report form (eCRF) or central laboratory. The analysis models for efficacy endpoints will use the stratification factors as collected in the database.

For continuous analyses of HbA1c, the stratification factor of HbA1c stratum (baseline) will not be included. Instead, the continuous value of baseline HbA1c will be included in the analysis models.

Other analyses will include the stratification factors as noted in Sections 6.11 and 6.12.

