#### 6.11.2. Analyses of Multiplicity Adjusted Objectives

[figure not shown]
A graphical approach for multiple comparisons (Bretz et al. 2011) will be used to strongly control the overall Type I error (2-sided alpha level of 0.05) for testing the treatment effect for the primary and the following multiplicity adjusted objectives: superiority of LY900014 compared with insulin lispro for (H2) 1-hour postprandial plasma glucose (PPG) excursion at the study primary endpoint, (H3) 2-hour PPG excursion at the study primary endpoint, and (H4) change from baseline to the study primary endpoint in HbA1c.

[figure not shown]
The graphical testing scheme for this study is displayed in Figure 6.1. All the hypotheses are connected by lines with arrowheads indicating the directions of testing paths. The initial allocation of study total alpha for each hypothesis is located within the same node of the hypothesis. In this

study, the study total alpha level (0.05) will be all used for the primary objective (H1) in the initial step. In this study, the study total alpha level (0.05) will be all used for the primary objective (H1) in the initial step. Then, the study total alpha level (0.05) will be allocated to other objectives according to the values of transition weights shown above the connecting lines in the figure once H1 is met. If 1 of the remaining objectives is successfully demonstrated with the given alpha level, its alpha will be allocated to the rest of objectives by the transition weights in the paths. The iterative test procedure continues until none of the remaining objectives can be demonstrated with their preserved alphas or all objectives are demonstrated successful.

An ANCOVA model with strata (country, type of basal insulin, use of metformin at study entry and HbA1c stratum) and treatment as fixed effects and baseline as a covariate will be used to analyze the 1-hour and 2-hour PPG excursions for data collected prior to discontinuation of IP. However, if the percentage of the patients with missing MMTT data at baseline is higher than 15%, a constrained longitudinal data analysis model (Liu et al. 2009; Lu 2010) will be used instead.

The superiority testing on change from baseline to the study primary endpoint in HbA1c will be assessed by the same analysis used for the primary objective. If the p-value is less than the alpha level allocated by the graphical approach, the superiority of LY900014 to insulin lispro will be achieved.

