#### 6.11.3. Additional Analyses of the Primary Outcome

The primary MMRM analysis model will be repeated using the PP and Completer populations as a sensitivity analysis. If the conclusion differs from that of all randomized patients, the data and analyses will be further investigated.

A secondary analysis model will be an ANCOVA for HbA1c change from baseline to the study primary endpoint, using the model with strata (country, type of basal insulin, use of metformin at study entry) and treatment as fixed effects and baseline as a covariate. Missing endpoints will be imputed using the LOCF approach using postbaseline data only.

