Treatment comparisons for the proportion of patients with HbA1c <7.0% and  $\le 6.5\%$  will be analyzed using a longitudinal logistic regression with repeated measurements conducted by a generalized linear mixed model including independent variables of treatment, baseline HbA1c value, visit, baseline HbA1c-by-visit interaction, and treatment-by-visit interaction. An unstructured covariance structure will be used. As a sensitivity analysis, the proportion of patients with HbA1c <7.0% and  $\le6.5\%$  at Week 26 (Visit 18), imputed using LOCF, will be compared using a logistic regression model with terms for treatment and baseline HbA1c value.

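### Free improvement, not an error: the primary MMRM fits one baseline HbA1c slope for Weeks 4, 8, 12 and 26, while H1 and H4 use only Week 26; a baseline-by-visit term would give Week 26 its own slope.

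*SAP*

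**What the plan says.** SAP 6.11.1 specifies a repeated-measures model for change in HbA1c with unstructured covariance. Its fixed effects are treatment, three stratification factors, "visit, and treatment-by-visit interaction, as well as the continuous, fixed covariates of baseline value". Protocol 10.3.1 has the same terms: "visit, and treatment-by-visit interaction, as well as the continuous, fixed covariate of baseline value". Neither lists a baseline-by-visit interaction.

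SAP Table 6.2 gives the post-baseline records as "Visits 11, 13, 15, and 18 prior to discontinuation of IP", and the Schedule of Activities places those visits at Weeks 4, 8, 12 and 26. SAP 6.2 explains why the HbA1c stratum is left out of this model: "Instead, the continuous value of baseline HbA1c will be included in the analysis models". That substitution is sensible.

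H1 is judged on the Week 26 contrast. For H4, SAP 6.11.2 says superiority "will be assessed by the same analysis used for the primary objective". Planning (SAP 5.2) rests on "a standard deviation (SD) of 1.1%, approximately 298 completers (149 in each treatment group) will provide 87% power" with a margin of 0.4%.

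Elsewhere, the longitudinal logistic model for the HbA1c targets (SAP 6.11.5) does include "visit, baseline HbA1c-by-visit interaction, and treatment-by-visit interaction".

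**The concern.** With baseline as a main effect, the fitted slope is a compromise over four visits. Generalised least squares weights the visits by their precision and correlation, so if early HbA1c changes vary less, Week 4 can dominate the slope used to adjust Week 26.

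The slopes could well differ. Week 4 HbA1c still largely reflects glycaemia in the lead-in. Prandial titration runs to Week 12 (Protocol 5.1), and Protocol 5.4 describes the Week 26 value as reflecting the later, stable-dose period. This is inference: no document gives a slope for any visit.

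At stake is mainly precision. A wider Week 26 interval makes noninferiority slightly harder to show and costs H4 a little power. A second, conditional issue is robustness. SAP 6.3 relies on the mixed model being consistent when data are missing at random, which also requires the mean model to be right, and SAP 6.11.4 plans no sensitivity analysis for missing data.

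**Working it through.** **The plan's own figure.** With SD 1.1, 149 per arm, margin 0.4 and true difference 0 (SAP 5.2):
- SE = 1.1 × √(2/149) = 0.1274.
- Half-width of the 95% interval = 0.2508.
- Power = 87.9% (noncentral t, 296 df) or 88.1% (normal). The stated 87% is reproduced.

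**Assumed inputs, not in the documents.** Baseline SD 0.8. Residual SDs 0.52/0.71/0.84/1.10 at Weeks 4/8/12/26, with Week 26 set to the planning SD. Correlation 0.75 per 8 weeks. Five sets of true slopes.

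**Formula.** Let b be the vector of true slopes and S the residual covariance. The common slope tends to β = (1′S⁻¹b)/(1′S⁻¹1). The model-reported Week 26 variance is multiplied by 1 + Var(baseline) × (b26 − β)² / (residual variance at Week 26).

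**Weights.** The inputs give visit weights of 1.354, −0.336, −0.085 and 0.067. Week 26 contributes almost nothing to its own adjustment.

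**Worked case, slopes −0.08/−0.18/−0.28/−0.42.**
- β = 1.354(−0.08) − 0.336(−0.18) − 0.085(−0.28) + 0.067(−0.42) = −0.052.
- Gap at Week 26 = −0.42 + 0.052 = −0.368.
- Inflation = 0.64 × 0.368² / 1.21 = 7.2%.
- Half-width cost = 0.2508 × (√1.072 − 1) = 0.009 HbA1c points.

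**All five cases.** The last three columns come from 12,000 simulated trials per case: 350 randomised within the 8.5% strata, 15% random dropout, true difference 0, other strata omitted. Ratios are common slope over visit-specific slope.

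| Slope, Week 4 to 26 | Analytic inflation | Half-width cost | Model variance ratio | Sampling variance ratio | H1 power, common / own slope |
|---|---|---|---|---|---|
| −0.20 throughout | 0% | 0.0000 | 1.001 | 0.999 | 88.9 / 88.9% |
| −0.15 to −0.25 | 0.6% | 0.0008 | 1.007 | 1.003 | 89.2 / 89.4% |
| −0.30 to −0.18 | 0.9% | 0.0012 | 1.011 | 1.002 | 88.9 / 89.2% |
| −0.08 to −0.28 | 2.5% | 0.0031 | 1.026 | 1.007 | 88.7 / 89.4% |
| −0.08 to −0.42 | 7.2% | 0.0088 | 1.072 | 1.038 | 87.3 / 89.3% |

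Coverage was 0.950 to 0.955 for both models, and mean estimates were within 0.002 of zero. Sampling variance rises less than model-reported variance because stratifying on HbA1c limits baseline imbalance. A hypothetical H4 test with 80% power would have 80.0, 79.8, 79.7, 79.2 and 77.6% in the five cases. Alpha 0.05 is assumed there, since the testing figure is not shown.

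**Sensitivity to inputs.** Over 36 sets (baseline SD 0.7-0.9, four SD profiles from steep to flat, correlation 0.6-0.9), the −0.28 case ranged from 0.3 to 5.3% (median 1.4%) and the −0.42 case from 1.0 to 15.1% (median 3.9%). With the SD flat at 1.1 and correlation 0.75, the weights become 0.39/0.05/0.11/0.45 and the two steepest cases fall to 0.5% and 1.4%.

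**Bias.** A separate set of simulated fits (residual SDs 0.45/0.70/0.85/1.10; 300 to 400 trials per setting) used steeper slopes, −0.10 to −0.45 and −0.05 to −0.60. When dropout depended on the previous HbA1c value alike in both arms, bias was below 0.01 for both models. When dropout depended strongly on baseline in opposite directions by arm (about 18% dropout, an extreme case), the common slope was biased by 0.09 and 0.14 points; the visit-specific slope stayed within 0.01. A large-sample calculation with the −0.42 slopes gave about zero for dependence alike in both arms, 0.026 for strong dependence in one arm only, and 0.049 for strong and opposite dependence.

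**The case against.** The strongest reply is that this is a modelling preference. The model is prespecified and identical in both documents, and no figure is wrong. The gain depends on slopes the documents do not give. The size depends on the assumed SD profile, as the flat-SD result shows, and in four of the five cases the half-width cost is at most 0.003 points against a 0.4 margin. The supportive ANCOVA in SAP 6.11.3 already fits a slope at the endpoint alone, though with LOCF. Nearly all of this stands, which is why the point is optional. What remains is that the term needs no new data and cost nothing measurable when slopes were equal.

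A reader might go further in three ways, none of which the documents support:
- **That the SAP contradicts itself**, because the responder model has the interaction. Different models may carry different terms; its presence shows only that the term is feasible with these data.
- **That the trial is underpowered, or could be materially smaller.** Simulated H1 power with the common slope was 87.3% or higher in every case in the table. Large savings appear only with much steeper assumed slopes.
- **That the primary estimate is biased.** That needs both slope drift and baseline-dependent dropout that differs by arm. The documents indicate neither, and the double-blind design gives no particular reason to expect the second.

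**Conclusion.** The point holds as an optional refinement. The current model is valid. A common slope may cost Week 26 precision if slopes differ by visit: about 0-3% of model-reported variance for equal to moderate drift at the central inputs, and about 1-15% for steep drift over the range examined. The upper figures require early-visit SDs well below the Week 26 SD. In the tabulated cases this is at most 0.009 HbA1c points of half-width and about 2 percentage points of H1 power. Every slope, early-visit SD and correlation is an assumption, as is reading 1.1 as the Week 26 residual SD.

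The absence of bias is conditional on dropout that is random or depends on baseline alike in both arms. Outside that condition, the visit-specific slope adds protection as well as precision.

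**What to change.** Before unblinding, add a baseline HbA1c-by-visit interaction (3 df) to the primary model in SAP 6.11.1. The documents do not show whether unblinding has occurred. Carry the term to:
- H4 (SAP 6.11.2);
- the repeats in SAP 6.11.3, where "The primary MMRM analysis model will be repeated using the PP and Completer populations as a sensitivity analysis", and the COVID-19 repeat of the MMRM (SAP 7.6);
- the longitudinal HbA1c analysis (SAP 6.11.5);
- the HbA1c subgroup models by antibody status (SAP 6.12.7.1) and in SAP 6.13.1, except the HbA1c-stratum subgroup, where baseline HbA1c is deliberately dropped.

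State whether the analogous secondary models for 1,5-AG, SMBG and insulin dose (SAP 6.11.5) follow suit. Record the departure from the Protocol 10.3.1 model and the reason, as SAP 6.1 provides, and say whether it changes a principal feature and so needs a protocol amendment.

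The statistical cost is three parameters with about 350 patients. With equal slopes the simulated sampling-variance ratio was 0.999 (SE 0.001), a loss of about 0.1% from the extra term. The practical cost is SAP wording in several sections, programming, and possibly an amendment. SAP Version 2 already changed covariates in the hypoglycaemia models through a SAP revision. That shows the route exists, but it was a removal made because of outliers and did not touch the primary model.

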#### 6.11.2. Analyses of Multiplicity Adjusted Objectives

[figure not shown]
A graphical approach for multiple comparisons (Bretz et al. 2011) will be used to strongly control the overall Type I error (2-sided alpha level of 0.05) for testing the treatment effect for the primary and the following multiplicity adjusted objectives: superiority of LY900014 compared with insulin lispro for (H2) 1-hour postprandial plasma glucose (PPG) excursion at the study primary endpoint, (H3) 2-hour PPG excursion at the study primary endpoint, and (H4) change from baseline to the study primary endpoint in HbA1c.

[figure not shown]
The graphical testing scheme for this study is displayed in Figure 6.1. All the hypotheses are connected by lines with arrowheads indicating the directions of testing paths. The initial allocation of study total alpha for each hypothesis is located within the same node of the hypothesis. In this

study, the study total alpha level (0.05) will be all used for the primary objective (H1) in the initial step. In this study, the study total alpha level (0.05) will be all used for the primary objective (H1) in the initial step. Then, the study total alpha level (0.05) will be allocated to other objectives according to the values of transition weights shown above the connecting lines in the figure once H1 is met. If 1 of the remaining objectives is successfully demonstrated with the given alpha level, its alpha will be allocated to the rest of objectives by the transition weights in the paths. The iterative test procedure continues until none of the remaining objectives can be demonstrated with their preserved alphas or all objectives are demonstrated successful.

An ANCOVA model with strata (country, type of basal insulin, use of metformin at study entry and HbA1c stratum) and treatment as fixed effects and baseline as a covariate will be used to analyze the 1-hour and 2-hour PPG excursions for data collected prior to discontinuation of IP. However, if the percentage of the patients with missing MMTT data at baseline is higher than 15%, a constrained longitudinal data analysis model (Liu et al. 2009; Lu 2010) will be used instead.

The superiority testing on change from baseline to the study primary endpoint in HbA1c will be assessed by the same analysis used for the primary objective. If the p-value is less than the alpha level allocated by the graphical approach, the superiority of LY900014 to insulin lispro will be achieved.

